7.2.3 Safety Analysis Set (SAF)

For the statistical summary of the safety data, the safety analysis set (SAF) will be used. The SAF consists of all patients from whom at least 1 ELIGARD® injection is received and any follow-up safety information is available.

7.2.4 Pharmacokinetic Analysis Set (PKAS)

Not applicable.

7.2.5 Pharmacodynamic Analysis Set (PDAS)

Not applicable.

7.3 Demographics and Other Baseline Characteristics

Demographics and other baseline characteristics will be summarized for the SAF and PPS. Descriptive statistics will include number of patients, mean, SD, minimum, median and maximum for continuous endpoints, and frequency and percentage for categorical endpoints.

7.4 Analysis of Efficacy

Efficacy analysis will be conducted on the FAS and PPS. The interpretation of results from statistical tests will be based on the FAS. The PPS will be used to assess the robustness of the results from the statistical tests based on the FAS.

7.4.1 Analysis of Primary Endpoint

Not applicable as the primary analysis of this study is a safety analysis.

7.4.2 Analysis of Secondary Endpoints

Descriptive statistics will be presented for the following:

- Percentage of patients with Testosterone <20, 20-50 and >50 ng/dL at 1 year and at 1.5 years
- Time to PSA progression: calculated from date of first administration of ELIGARD® 22.5 mg to PSA progression
- PSA progression will be defined as a 25% or greater increase and an absolute increase of 2 ng/mL or more from the nadir is documented, which is
 - Confirmed by a second value obtained 3 or more weeks later
 - If not done based on standard clinical practice, the confirmatory PSA measurement should be performed at the next routine study visit.

Note: The aim is to detect time to PSA progression and not to assess whether the patient has progressed to CRPC. Imaging and other modalities should be used to determine if the patient has moved to CRPC, which is outside the scope of this study

- HRQoL: (EORTC QLQ-PR25 and EQ-5D-5L) at baseline and following scheduled visits as well as change from baseline

7.4.3 Analysis of Exploratory Endpoints

Not applicable as there are no exploratory objectives in this study.

7.5 Analysis of Safety

7.5.1 Adverse Events

AEs will be coded using the Medical Dictionary for Regulatory Activities (MedDRA). The number and percentage of AEs, SAEs, Severe AEs (defined as AEs graded ≥ 3 according to NCI-CTCAE guidelines Version 4.03), AEs leading to treatment discontinuation, and ELIGARD®-related AEs will be summarized by System Organ Class (SOC), Preferred Term (PT). The number and percentage of AEs by severity will also be summarized. AEs that occur after

receiving CRPC management will be presented separately. All AEs, including information described in following subsections, will be listed.

7.5.1.1 Incidence of ELIGARD® Related Adverse Events

ELIGARD®-related AEs are AEs that are reported to be related to ELIGARD® (possible or probable) as determined by the investigator.

All ELIGARD®-related AEs will be summarized according to their severity, NCI CTCAE Grade, outcome, course of event, seriousness, action taken with ELIGARD® and treatment required to manage the AE for SAF set.

To analyze the incidence of ELIGARD®-related AEs and SAEs during the observation period, 2-sided 95% symmetric CIs of incidence rates based on normal approximation will be presented after adjusted for a finite sample size of 10000. All SAF subjects will be counted, and separate summaries shall be performed for ELIGARD®-related AEs and SAEs.

Time to first occurrence of ELIGARD®-related AEs and SAEs will be presented using Kaplan-Meier (KM) plots. If applicable, estimated median time to first event together with a 95% CI will be prepared. In addition, KM estimates of incidence rates of ELIGARD®-related AEs and SAEs will be summarized at each scheduled visit time-point, together with a 95% CI.

Of note, summaries of ELIGARD®-related AEs and SAEs that occurred after receiving CRPC management will be presented separately.

Details of statistical analyses for primary safety endpoint will be described in the statistical analysis plan.

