1 INTRODUCTION

1.1 Background

Epidemiology of Prostate Cancer

Prostate cancer (PC) is the second most common malignancy in men with nearly 1 million new cases being diagnosed worldwide [Baade et al, 2013]. The analysis of GLOBOCAN data showed that more developed countries have much greater 5-year prevalence and incidence rates than underdeveloped countries [Crawford, 2003].

Approximately 14% of all prostate cancers diagnosed worldwide in 2008 were within the Asia-Pacific region. Differences in prostate cancer incidence rates and prevalence rates exist both regionally within Asia and between Asia and Western nations. The reported incidence of prostate cancer among all cancers affecting men in Asia varies by country; prostate cancer is the third most commonly diagnosed male cancer in Singapore and Malaysia, fourth in Japan and Thailand, fifth in South Korea, sixth in China, and ninth in India [Crawford, 2003]. The overall incidence of, and mortality from, prostate cancer in Asian countries are lower than the rates observed in cohorts of migratory Asians in Western countries, and considerably lower than those in native Western individuals. However, there is an increase in prostate cancer incidence in the Asia-Pacific region, where Hong Kong and Singapore (Chinese population only) recorded annual increases of around 6% for males of all ages between 1998-2009 and 1980-2002, respectively [Baade et al, 2013]. Smaller, but still significant, increases in prostate cancer incidence rates were found for males of all ages in the Philippines and Thailand (3% per year increase between 1983-2002 and 1983-2009, respectively) [Baade et al, 2013].

Prostate cancer is the most common cancer in elderly males. The incidence rates of prostate cancer increase with age. It is relatively rare for prostate cancer to be diagnosed in men <50 years of age, but after this age, the incidence and mortality rates increase exponentially [Baade et al, 2013]. In some Asian countries (Japan, Hong Kong and South Korea) the increase was more pronounced after 60 years of age [Baade et al, 2013]. The majority of cancer cases are diagnosed between 50-79 years of age [Baade et al, 2013].

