7.1 Sample Size

This study targets to enroll approximately 107 prostate cancer patients.

The sample size was calculated based on the estimated percentage of ELIGARD[®]-related AEs, as well as the desired width of its 95% CI. Prior clinical studies on ELIGARD[®] have shown an ELIGARD[®]-related AEs rate of around 50% of patients during a six-month treatment period [ELIGARD Investigator's Brochure, June 2008; Tombal & Berges, 2007]. With the assumption that the percentage of ELIGARD[®]-related AEs will be 50%, a sample size of 96 completed patients is sufficient for estimating a Wald 95% CI with a width of 20% (+/- 10% from the middle), based on a finite population correction, with factor N=10,000.

Therefore, the total sample size of this study, assuming a drop-out rate of 10%, is 107 patients.

PASS 14 Power Analysis and Sample Size Software (2015) version number 14.0.2 was used in the sample size calculation (NCSS, LLC, Kaysville, Utah, USA, ncss.com/software/pass).

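### The primary-endpoint confidence interval and the sample size use a finite population correction for 10,000 that the protocol neither defines nor justifies; it is invalid here, but narrows the interval by only about 0.5%.

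*Protocol*

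**What the plan says.** The correction appears in two roles.

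- **Analysis.** Section 7.5.1.1 fixes the interval for the incidence of related AEs and related SAEs: "2-sided 95% symmetric CIs of incidence rates based on normal approximation will be presented after adjusted for a finite sample size of 10000". The same section sets the denominator: "All SAF subjects will be counted".
- **Sample size.** Section 7.1, repeated in the Synopsis, says that "a sample size of 96 completed patients is sufficient for estimating a Wald 95% CI with a width of 20% (+/- 10% from the middle". The anticipated incidence is 50%, and the calculation is described there as "based on a finite population correction, with factor N=10,000". The figure for enrolment is then given as follows: "assuming a drop-out rate of 10%, is 107 patients".

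Neither section says what the 10,000 are or where the number comes from. Section 7.5.1.1 calls it a sample size, whereas Section 7.1 treats it as a population size; the sample itself is about 107.

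Three other places bear on whether the correction can apply:

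- Section 2.1 sets the primary objective as the safety profile in ethnic Asian prostate cancer patients, with no limit to a listed group.
- Section 2.2.1 plans about 20 centres in 8 countries.
- Section 3.1 enrols eligible patients consecutively within each site and competitively across sites.

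**The concern.** A finite population correction reduces the variance because, when a sizeable part of a closed population has been observed, less of it remains unknown. It needs three things: a population of known size N, a random draw from it without replacement, and a conclusion confined to those N people. The protocol supplies none of them. The population is undefined, the patients are whoever presents and consents at the chosen sites, and the conclusion is meant for Asian patients who will receive the drug later as well as those enrolled.

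The correction factor is below 1 for any sample larger than one, so the error can go in one direction only: the interval is too narrow. This interval carries the main result of a descriptive safety study in which Section 7 rules out formal comparisons. An unexplained constant that tightens it is hard to defend to a regulator or a journal. Leaving details of the primary safety analysis to the SAP does not remove the problem, because the protocol itself fixes the rule.

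**Working it through.** **Inputs.** From Section 7.1: anticipated proportion p = 0.50, target half-width h = 0.10, population N = 10,000, drop-out 10%, 96 completers and 107 enrolled. From Section 7.5.1.1: a two-sided 95% normal-approximation interval (z = 1.95996) on all patients in the safety analysis set, so up to 107 if every enrolled patient qualifies.

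**Step 1: reproduce the stated size.**

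- Uncorrected: n0 = z² p(1−p)/h² = 1.95996² × 0.25 / 0.01 = 96.04.
- Corrected: n = n0 / (1 + (n0 − 1)/N) = 96.04 / (1 + 95.04/10,000) = 95.13, rounded up to 96.
- Enrolled: 96 / 0.9 = 106.7, rounded up to 107.

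Both stated figures are reproduced.

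**Step 2: size without the correction.** The formula gives 96.04. Ordinary rounding leaves 96 and 107. Strict rounding up gives 97, and 97 / 0.9 = 107.8, so 108 enrolled. The size moves by at most one patient.

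**Step 3: effect on the interval.** Half-width = z √(p(1−p)/n), multiplied by √((N − n)/(N − 1)) when the correction is applied. The factor is √(9,904/9,999) = 0.9952 at n = 96 and √(9,893/9,999) = 0.9947 at n = 107.

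| n | Incidence | Half-width with correction (points) | Without (points) |
|---|---|---|---|
| 96 | 50% | 9.954 | 10.002 |
| 107 | 50% | 9.423 | 9.474 |
| 107 | 70% | 8.637 | 8.683 |
| 107 | 5% | 4.108 | 4.130 |

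At 50% and n = 107 the difference is 9.474 − 9.423 = 0.05 point on each side, and 1 − 0.9947 is about 0.5% of the width.

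**Step 4: coverage.** Exact binomial coverage of the interval at n = 107, with and without the correction, is 94.7% and 94.7% at a true incidence of 50%, 94.2% and 95.2% at 70%, and 90.0% and 90.0% at 5%. Removing the correction does not lower coverage at any of these values, and raises it at one.

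**The case against.** The strongest reply is that nothing depends on this. The study tests no hypothesis, no threshold is tied to the interval, and the limits move by about 0.05 point. That is fair on size and is why the point is minor. It does not make the rule right, and removing it costs nothing.

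Four stronger readings are tempting, and the documents do not support them.

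- **That 96 and 107 are too favourable.** Without the correction 96 completers give ±10.002 points, which is 10% at the precision stated. The primary interval also counts the whole safety analysis set, not only completers; with 107 patients the uncorrected half-width of 9.47 is inside the target. Section 7.1 enrols approximately 107, so a possible difference of one patient is immaterial.
- **That no population of 10,000 exists.** The protocol only leaves it undefined. It gives no count of eligible men starting this treatment in the 8 countries, so existence can be neither shown nor excluded.
- **That the true population is more than ten times larger.** Section 1.1 mentions "nearly 1 million new cases being diagnosed worldwide" and says "Approximately 14% of all prostate cancers diagnosed worldwide in 2008 were within the Asia-Pacific region"; the product is about 140,000. That applies a 2008 share to a total with no stated year, and it counts all stages across a region wider than the trial's countries. Even at N = 140,000 the formula gives 95.97, so still 96 and 107.
- **That the Kaplan-Meier intervals conflict with this one.** Section 7.5.1.1 asks for 95% intervals around those estimates without naming a variance method, so a conflict would be inferred from silence. The two variances differ in any case, because the Kaplan-Meier estimate handles censoring.

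**Conclusion.** The correction should not be used. This rests on what the protocol does say: an open target population, consecutive and competitive enrolment at selected centres, and no definition of the 10,000. It does not depend on any estimate of how many eligible patients there are, because the sampling and the target rule the correction out whatever N is.

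The consequence is an interval for the primary endpoint that is about 0.5% too narrow, or 0.05 point on each side at an incidence of 50% with 107 patients. The sample size is sound as it stands. The figure of about 9.5 points assumes that all 107 enrolled patients enter the safety analysis set; with 96 it would be 10.0. Severity is minor.

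**What to change.** 1. In Section 7.5.1.1, delete the adjustment to 10,000 and compute the intervals for related AEs and related SAEs without it. This also removes the mislabelling of 10,000 as a sample size.
2. In Section 7.1 and the Synopsis, delete the finite-population clause. Keep 96 completers and 107 enrolled, and give the basis as an uncorrected requirement of 96.04, that is ±10.0 points at 50%.
3. Add that the expected half-width is about 9.5 points if all 107 patients are in the safety analysis set.
4. Make sure that the SAP follows the same rule.

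The cost is a short wording change in three places and a primary interval about 0.05 point wider on each side. No patients are added and study conduct does not change.

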Prostate cancer rates are highest in Western countries and lowest in Asian countries [Sim & Cheng, 2005]. However, Asian populations generally have higher proportions of men with advanced stage prostate cancer compared with Western populations, despite overall reports of prostate cancer incidence being substantially lower in the former [Ito, 2014]. The epidemiological pattern of prostate cancer in Asia suggests that prostate cancer often goes unnoticed, at least until later stages of the disease, possibly owing to restricted access to screening programs and urology clinics in Asian countries [Ito, 2014].

There was a large disparity in the survival prospects on men with prostate cancer throughout the Asia-Pacific region. Five-year relative survival estimates of 85% and above were reported in New Zealand, Australia, Japan, Singapore and South Korea [Baade et al, 2013]. This contrasts with estimated 5-year survival rates of between 30% to 40% in parts of China and Thailand [Baade et al, 2013].

With the expected increases in life expectancy of men and in the incidence of prostate cancer [Center et al, 2012], the disease's economic burden is also expected to increase substantially. In Europe, it is estimated that the total economic costs of prostate cancer exceed €8.43 billion, with a high proportion of the costs of prostate cancer care occurring in the first year after diagnosis [Mottet et al, 2006]. In European countries with available data (United Kingdom, Germany, France, Italy, Spain, Netherlands), this amounted to €106.7 – 179.0 million for all prostate cancer diagnosed in 2006 [Mottet et al, 2006].

In Asia, the population over 60 years old is about 4 times greater compared to those of North America and Europe [Zhang et al, 2011]. Given that life expectancy is expected to increase markedly in many parts of Asia over coming years, the burden of prostate cancer in this region is likely to increase in the future. Health problems will become a greater burden in Asian countries despite rapid socioeconomic growth.

It has been reported that patients with terminal prostate cancer show considerably decreased quality of life (QoL) for many years before death, owing to the adverse effects of long-term systemic treatments as well as physiological and psychological impairment resulting from progression of local disease and distant metastases [Ito, 2014].

ELIGARD[®] (leuprolide acetate for injection)

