3.3 Exclusion Criteria

1. Patient with castrate resistant prostate cancer (CRPC)
2. Patient who previously underwent bilateral orchiectomy
3. Patient who has received prior treatment with LHRH analogues
4. Prior or concomitant treatment with systemic chemotherapy. A patient where there is a likelihood to receive systemic chemotherapy should not be enrolled
5. Life expectancy of < 1 year due to comorbidities
6. Participation in another interventional clinical trial within 1 month prior to study entry or during the duration of the study
7. Physician is planning to give the patient intermittent ADT at the time of study entry
8. Patient receiving non-palliative radiotherapy within 3 months prior to study entry
9. Patient receiving adjuvant ADT in combination with definitive radiotherapy
10. Patient with metastatic hormonal treatment-naive prostate cancer, for whom chemo-hormonal treatment (combination of Docetaxel and ADT) is indicated.
11. Patient with hypersensitivity to GnRH, GnRH agonist analogs or any of the components of ELIGARD®
12. Patient with any contraindication for ELIGARD® use based on local prescribing information

While patients enrolled or expected to be enrolled in clinical trials of investigational therapy are not allowed, their participation in this interventional study will not preclude them from future participation in other non-interventional studies.

Waivers to the exclusion criteria will NOT be allowed.

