6 DISCONTINUATION

6.1 Discontinuation of Individual Patients

A discontinuation is a patient who enrolled in the study and for whom study treatment is permanently discontinued prematurely for any reason.

A patient is free to withdraw from the study for any reason, at any time, without reason for doing so and without penalty or prejudice.

A patient will be discontinued from the study in the case of:

1. Withdrawal of consent - patient decision to withdraw from further participation in the study
2. Patient safety is at risk (at the discretion of the treating physician)
3. Patient develops CRPC as determined by European Association of Urology (EAU) Prostate Cancer Guidelines 2016
4. Patient is lost to follow-up
5. Patient death during the study
6. Patient misses consecutive visit periods (window \pm 14 days) during the study
7. Patient who is less than 80% compliant with the dosage regimen for any 2 consecutive visit periods (window \pm 14 days) during the study.
8. Site terminated by the Sponsor
9. Study terminated by the Sponsor
10. Cessation of treatment with ELIGARD[®] (at the discretion of the treating physician). The reasons for stopping treatment will be noted (e.g., PSA progression, radiographic progression, clinical progression, AE, drug administration issues, other).
11. Patient takes prohibited medications as described in Section 5.1.6 and Section 12.2

For patients that discontinue from the study, the reason for discontinuation should be recorded in the eCRF. Patients that discontinue will have an Early Withdrawal visit 3 months after the last administration of ELIGARD[®] for safety assessment. At the end of a patient's involvement in this study, the Investigator must ensure that all outstanding data entry is entered in the eCRF unless the patient withdrew consent for their data to be used.

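### The visit-wise Kaplan-Meier incidence rates in 7.5.1.1 would modestly overstate cumulative incidence if deaths are censored; the main crude proportion is not affected

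*Protocol*

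**What the plan says.** Protocol 7.5.1.1 summarises the incidence of ELIGARD-related AEs and SAEs in two ways.

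- **Main figure.** This is a crude proportion: "2-sided 95% symmetric CIs of incidence rates based on normal approximation will be presented after adjusted for a finite sample size of 10000". Its denominator is the whole safety analysis set: "All SAF subjects will be counted, and separate summaries shall be performed for ELIGARD®-related AEs and SAEs". Section 7.1 sizes the trial on this proportion.
- **Time-to-event figures.** "Time to first occurrence of ELIGARD®-related AEs and SAEs will be presented using Kaplan-Meier (KM) plots", with a median time to first event where it can be estimated. As a further summary, "KM estimates of incidence rates of ELIGARD®-related AEs and SAEs will be summarized at each scheduled visit time-point", each with a 95% CI. The Synopsis repeats this use of Kaplan-Meier for incidence at the scheduled time-points.

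Section 6.1 lists "Patient death during the study" among the reasons for discontinuation. The protocol does not say how a death enters the Kaplan-Meier analysis and names no competing-risk method. Section 7.5.1.1 closes with "Details of statistical analyses for primary safety endpoint will be described in the statistical analysis plan".

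**The concern.** The endpoint is the first related AE or SAE. Death is not part of it, so the ordinary Kaplan-Meier convention censors a man who dies without a related event and treats him as if he would have gone on to have events at the survivors' rate. One minus Kaplan-Meier is then the risk in a hypothetical population in which nobody dies. Calling it an incidence rate invites the reader to take it as the proportion of these patients who had the event by that visit.

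Deaths within 18 months are plausible. Metastatic disease is eligible (3.2), and short life expectancy is an exclusion only in the form "Life expectancy of < 1 year due to comorbidities". The error would run in one direction, would grow with follow-up time and would not be reflected in the confidence intervals. These are also the only visit-specific incidence figures in 7.5.1.1, so they are what a reader would cite for incidence by Month 12 or Month 18.

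**Working it through.** **1. The plan's own figure (7.1).** Inputs: 50% event level, half-width 10 points, 95% confidence, finite population 10,000, 10% drop-out.

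- n0 = 1.96² × 0.5 × 0.5 / 0.1² = 96.04
- With the correction: 96.04 / (1 + 95.04/10,000) = 95.13, rounded up to 96
- 96 / 0.9 = 106.7, rounded up to 107

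The stated 96 and 107 reproduce. They rest on the crude proportion, so this point does not touch them. The 10-point half-width is used below only as a yardstick.

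**2. The two quantities.** Let a(t) be the hazard of a first related event and m the hazard of death without one, with A(t) the cumulative hazard of a(t).

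- One minus Kaplan-Meier with deaths censored: 1 − exp(−A(t))
- Cumulative incidence: the integral from 0 to t of a(u) × exp(−A(u) − m·u) du

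The second contains the extra factor exp(−m·u) ≤ 1, so it can never exceed the first. This fixes the direction.

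**3. Assumptions.** One minus Kaplan-Meier at Month 18 is set at 50%, the event level in 7.1, so A(18) = ln 2 = 0.693. The death hazard is constant: m = −ln(1 − D)/18 for 18-month mortality D. The protocol gives no D for this trial, so a range is used.

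- **D = 5% and 10%:** assumed working values.
- **D of about 30%:** an upper bound from Protocol 1.1, which cites "estimated 5-year survival rates of between 30% to 40% in parts of China and Thailand". At constant hazard, 30% five-year survival gives 1 − 0.30^(1.5/5) = 30.3%. The 85% relative survival cited there for other countries gives, treated the same way, 1 − 0.85^0.3 = 4.8%.

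Two event timings bracket the answer.

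- **Even over 18 months:** a = 0.693/18 = 0.0385 per month.
- **All within the first 6 months:** a = 0.693/6 = 0.1155 per month. Section 7.1 describes the 50% as a six-month figure.

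**4. Calculation.** For a constant a up to time T, cumulative incidence = a/(a + m) × (1 − exp(−(a + m)T)). Example with D = 10%, so m = 0.00585 per month:

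- Even timing: 0.0385/0.0444 × (1 − 0.450) = 47.7%, an excess of 2.3 points
- Early timing: 0.1155/0.1214 × (1 − 0.4827) = 49.2%, an excess of 0.8 points

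| Assumed 18-month mortality | Excess, events within 6 months | Excess, events even over 18 months |
|---|---|---|
| 5% | 0.4 points | 1.1 points |
| 10% | 0.8 points | 2.3 points |
| 20% | 1.6 points | 4.6 points |
| 30.3% | 2.6 points | 7.2 points |

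Putting 70% of the event hazard in the first 3 months gives values in between: 0.5, 1.0 and 2.0 points at 5%, 10% and 20% mortality.

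**5. Related SAEs.** With an assumed event level of 5% to 10%, the excess is at most 0.5 points at 10% mortality and at most 1.6 points at 30%.

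**The case against.** Three stronger readings are tempting, and the documents support none of them.

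- **That the plan prescribes censoring at death.** It does not. No censoring rule is given, and 7.5.1.1 leaves the details to the SAP, which could supply one. What stands against this defence is that the protocol has already fixed both the estimator and its label, in two places. Under that estimator, censoring is what happens unless someone says otherwise.
- **That the primary safety result is overstated.** It is not. The main figure counts every patient in the safety analysis set, so a man who dies without an event stays in the denominator. The Kaplan-Meier figures are additional and descriptive, and no formal comparison is planned (Section 7). That the crude and Kaplan-Meier figures can differ is no defect either; they do so whenever follow-up is incomplete.
- **That an error of about 7 points should be expected.** This needs about 30% mortality and evenly spread events together. The survival figure behind it covers all stages, is the bottom of a 30% to 40% range, and concerns parts of China and Thailand; of these only Thailand is named among the participating countries in 2.2.1. The trial excludes castrate-resistant disease (3.3), discontinues men who develop it (6.1) and ends AE monitoring 3 months after the last dose (5.6.5), so many cancer deaths would fall outside observation. Deaths at that level also sit badly with the 10% drop-out allowance in 7.1. At the other end, the 85% is relative survival, not all-cause survival, so 4.8% understates total mortality to that extent.

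It is also fair to say that Kaplan-Meier with death censored is a legitimate description of time to first event if labelled as such. The fault lies in presenting it as incidence. Stopping for castrate-resistant disease, poor compliance or prohibited medication is not addressed for these curves either and may matter as much as death.

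**Conclusion.** The point holds in conditional form and is minor. If men who die without a related event are censored, the visit-wise Kaplan-Meier figures overstate cumulative incidence, with certainty as to direction. The likely size at Month 18 is about 0.4 to 2.3 points, with 2.6 to 7.2 points as an upper bound, against a planned half-width of 10 points. These sizes rest on a 50% event level, a constant death hazard and assumed mortality, since the protocol gives none for this trial. The crude proportion and the sample size stand unchanged.

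**What to change.** In 7.5.1.1 and the Synopsis, report the incidence of first related AE and first related SAE at each scheduled visit as Aalen-Johansen cumulative incidence with 95% CI. Take death before the first related event as a competing event and treat other ends of observation (Month 18, end of AE follow-up after stopping treatment, loss to follow-up) as censoring. The Kaplan-Meier plots and median time to first event may stay if they are labelled as estimates with death censored.

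The cost is a sentence in each place and slight extra programming. No new data are needed, because deaths and adverse events are already collected. Reported incidence at later visits will be slightly lower than Kaplan-Meier would show.
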